Indocyanine Green-guided Lymphadenectomy in Laparoscopic Total Mesorectal Excision for Low Rectal Cancer After Neoadjuvant Chemoradiotherapy

PIs and sub-investigators: [name], [name], [name], [name], [name]

Background

Cancer treatment is increasingly oriented toward a personalized medicine. In medical oncology, treatments are often targeted toward specific receptors and cellular pathways, while in surgical oncology a real personalized medicine approach is still a far objective. Indeed, lymph nodes dissection in colorectal cancer surgery is still based on traditional anatomical borders and recently it has been greatly extended routinely in all patients, since a greater harvesting of lymph nodes should mean more accurate pathologic staging and a better disease control.^{1,2}

Despite the correct rationale of this approach, it means to waive the “minimal effective treatment” concept in colorectal surgery, with a tout-court use of wide surgical procedures often burdened by a high intraoperative or postoperative complications rate.³

Currently, in rectal cancer surgery two major issues are still controversial, especially in patients treated by neoadjuvant chemoradiation:

1. The need for harvesting apical lymph nodes at the origin of inferior mesenteric artery for middle-low rectal cancer is still debated.⁴ Indeed, the excision of these lymph nodes could allow a more accurate staging, but the high ligation of inferior mesenteric artery leads necessarily to a greater colorectal resection due to the devascularization of the left colon, with a higher risk of anastomotic leakage and of hypogastric nerves injury. The recent HIGHLOW randomized clinical trial has been conducted on patients affected by rectal cancer, comparing those with a high vs. low ligation of the inferior mesenteric artery. The trial has demonstrated that disease control was similar between groups, but also that long-term genitourinary complications were much more frequent among patients with vessel ligation at the origin.⁵
2. Lateral pelvic lymph nodes dissection is another point of controversy for rectal cancer patients. Indeed, Japanese surgeons perform routinely this dissection, believing that possible residual disease in these lymph nodes is the major responsible for lateral recurrences.⁶ In Europe and in the USA this procedure is not routinely performed, since neoadjuvant chemoradiation is much more administered with a possible impact also on lateral pelvic nodes, also considering the low risk of lateral pelvic nodal metastases.

Based on data retrieved from the cohort of rectal cancer patients treated by neoadjuvant chemoradiation and surgery at the Colorectal Surgery of Fondazione IRCCS Istituto Nazionale dei Tumori (Milan, Italy) from 2011 to 2020, the mean number of harvested lymph nodes is 15.8 ± 7.7 . Recently, indocyanine green (ICG)-guided surgery has been introduced in routine clinical practice. ICG is a fluorescent tracer which can be detected by specific cameras for laparoscopic and open surgical procedures. Currently, ICG in colorectal surgery is mainly used to assess the adequate blood supply to the anastomosis.⁷ In other fields, the role of ICG-guided surgery has been explored for lymph nodes dissection such as in breast cancer surgery.⁸

Objectives and endpoints

The primary objective of the study is to assess if the total number of retrieved lymph nodes is superior with ICG-guided surgery compared to standard surgery, in rectal cancer patients undergoing neoadjuvant chemoradiation and subsequent surgery. The primary endpoint of the study is the mean total number of retrieved lymph nodes. Secondary endpoints are the following:

- 1) Number of harvested lymph nodes specifically at the origin of the inferior mesenteric artery
- 2) Number of harvested lateral pelvic lymph nodes
- 3) Intraoperative and postoperative complications rates
- 4) Mean duration of surgery
- 5) Mean duration of the postoperative hospitalization

Type of study

Interventional, non-pharmacological, single-arm study

Inclusion criteria

- Middle-low rectal adenocarcinoma
- Neoadjuvant chemoradiation
- Laparoscopic surgery
- Signed informed consent

Exclusion criteria

- Distant metastases at diagnosis

- Squamous cell carcinoma
- Peritoneal carcinomatosis
- Allergy to ICG

Methods

In all patients, a total volume of 2 mL of ICG (dilution: 5 mg/mL in 10 mL of sterile water) will be injected transanally, administering 0.5 mL of ICG in each peri-tumoral quadrant in the submucosa, 10 minutes before surgery. Surgery will be performed laparoscopically, and a dedicated camera with near-infrared filter will be used to intraoperatively detect ICG-fluorescent lymph nodes. ICG-guided surgery will consist of standard anterior rectal resection with total mesorectal excision, plus the selective excision of extra-mesorectal ICG-fluorescent lymph nodes (origin of the inferior mesenteric artery and/or lateral pelvic nodes). All the other treatments and follow up regimens will be according to the standard of care.

Statistical analysis

The sample size has been calculated based on feasibility criteria, since this is a pilot study. Thus, 30 patients will be accrued in 12 months, also considering a possible drop-out of 10%. The control group will be composed by 30 rectal cancer patients previously treated with neoadjuvant chemoradiation followed by standard surgery, possibly matched by propensity score,

References

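### The primary endpoint is a lymph node count with no masking of the person counting and no counting rule, so extra search effort in the ICG group alone could pass for an ICG effect

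*Combined protocol and SAP*

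**What the plan says.** Under Objectives and endpoints, the primary objective is to "assess if the total number of retrieved lymph nodes is superior with ICG-guided surgery compared to standard surgery", and "The primary endpoint of the study is the mean total number of retrieved lymph nodes". The Type of study section describes an "Interventional, non-pharmacological, single-arm study". The comparator appears only under Statistical analysis: "The control group will be composed by 30 rectal cancer patients previously treated with neoadjuvant chemoradiation followed by standard surgery, possibly matched by propensity score".

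Methods defines the ICG procedure as the standard resection with total mesorectal excision, plus targeted removal of fluorescent nodes outside the mesorectum (at the inferior mesenteric artery origin, the lateral pelvis, or both). Nodes at these two sites are also counted separately, as the first two secondary endpoints.

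The documents do not mention a pathologist, a node-search or specimen-handling standard, masking of the person who counts, or the source of the control counts. The one general sentence on standard of care, at the end of the first paragraph of Methods, covers treatments and follow-up. It does not address how the outcome is measured.

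**The concern.** A count of retrieved nodes reflects two things: the tissue the surgeon removes, and how thoroughly that tissue is searched. The plan varies the first and leaves the second uncontrolled. The ICG counts will be produced during an open study whose hypothesis is a higher count, while the controls were operated on beforehand. If knowing that a specimen is from the study prompts a harder search, the extra nodes arise in one group only and push towards the hypothesis.

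Propensity matching balances patient characteristics. It cannot correct a difference in how specimens are examined, and it is in any case only described as possible.

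The choice of total count adds to the exposure. The surgical addition lies outside the mesorectum, but the endpoint also includes the mesorectal specimen, which standard surgery removes too. Nodes found there by harder searching would be added to the same total as nodes obtained by the ICG-guided excision.

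**Working it through.** **The plan's own figure.** The Statistical analysis section says "The sample size has been calculated based on feasibility criteria, since this is a pilot study". It gives no effect size, test, alpha, sidedness or power, so there is no power calculation to reproduce. The only arithmetic available is the 10% drop-out: 27 / (1 − 0.10) = 30, so 30 enrolled is consistent with 27 evaluable.

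**Inputs from the documents**
- Reference count, from Background point 2: "the mean number of harvested lymph nodes is 15.8 ± 7.7". The ± is read as an SD; the text does not name it.
- Group sizes, from Statistical analysis: 30 ICG patients (27 if 10% drop out) and 30 controls.

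**Assumptions**
- Two-sided 5% test, with a one-sided 5% variant.
- Same SD in both groups, independent groups, normal approximation.
- No true ICG effect.
- A mean excess b of 1, 2 or 3 nodes per ICG patient from search effort alone. The documents give no value for b.

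**Standard error of the difference**
- 30 vs 30: 7.7 × √(1/30 + 1/30) = 1.99 nodes.
- 27 vs 30: 7.7 × √(1/27 + 1/30) = 2.04 nodes.

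**Difference needed for significance (two-sided 5%)**
- 30 vs 30: 1.96 × 1.988 = 3.9 nodes.
- 27 vs 30: 1.96 × 2.043 = 4.0 nodes.

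**Chance of a significant result favouring ICG:** 1 − Φ(1.96 − b/SE). For b = 2 with 30 vs 30: b/SE = 2/1.988 = 1.006; 1.96 − 1.006 = 0.954; 1 − Φ(0.954) = 0.170.

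| Assumed excess b (nodes) | As % of 15.8 | 30 vs 30, two-sided 5% | 27 vs 30, two-sided 5% | 30 vs 30, one-sided 5% |
|---|---|---|---|---|
| 0 | 0% | 2.5% | 2.5% | 5.0% |
| 1 | 6.3% | 7.3% | 7.1% | 12.7% |
| 2 | 12.7% | 17.0% | 16.3% | 26.1% |
| 3 | 19.0% | 32.6% | 31.2% | 44.6% |

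Drop-out hardly changes the result. The choice of test changes the level but not the pattern.

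**The case against.** The strongest reply is that the documents show silence, not bias. They do not describe the pathology work-up in either group, and that a count depends on search effort is general knowledge rather than something the plan states. The excess of 1 to 3 nodes is chosen, and 2 to 3 nodes is 13% to 19% of the reference mean, which is a lot to attribute to awareness alone. The study is a pilot sized on feasibility, so a false-positive rate is an imperfect measure of harm. All of this stands, and it limits the point to an unguarded risk of unknown size. It does not remove the point, because the plan states a superiority objective on this count.

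A second reply is that the secondary endpoints already allow a check: the total minus the inferior mesenteric and lateral pelvic counts approximates the mesorectal count, and an excess confined there would not match the added excision. That is correct, but the plan does not state this check or say how such a result would be read.

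A third reply is that masking is weakest where the planned effect lies, because separate containers of extra-mesorectal nodes may identify the procedure. It would also leave any change in pathology practice since the controls were treated. Both limits stand.

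A reader might infer that the control counts were taken from routine reports written when no study depended on them. The documents say only that these patients were previously treated; they do not give the source of the counts. A reader might also infer that the remedy is to forbid repeat search or fat clearance in ICG specimens. The documents do not support that either. They do not say whether these steps were part of the routine behind the control counts; if they were, a ban would lower ICG counts relative to controls, and it would interfere with diagnostic staging.

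**Conclusion.** The concern holds as a design omission that should be closed before specimens are read. The primary comparison sets an open prospective group against earlier patients on a count with no masking and no counting rule, and patient matching cannot repair a one-sided difference in search.

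Its size is unknown. Under the assumptions listed, a mean excess of 1, 2 or 3 nodes would raise the chance of a false favourable result from 2.5% to about 7%, 17% and 33%. These figures show sensitivity; they do not estimate what will happen. A reader might infer that ICG specimens will in fact be searched harder, or that a positive result would be an artefact. The documents support neither conclusion, and they offer no means of separating assessor awareness from a change in pathology practice over time.

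**What to change.** Add a short outcome-assessment paragraph to Methods, with a matching instruction to theatre and pathology:

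1. Send ICG-group specimens on the routine pathology form, labelled by anatomical site only, with no mention of ICG or the study.
2. Use the department's routine node search, with no study-specific search. Do not forbid any step that belongs to routine work-up.
3. Define the primary value in both groups as the count at first routine sign-out.
4. Report mesorectal and extra-mesorectal counts separately beside the total, and state in advance that an excess confined to the mesorectum will not automatically be read as the yield of the added extra-mesorectal excision.

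The cost is close to nil: one instruction and two extra lines in the results, with no additional reader or procedure. There are three downsides. Separate extra-mesorectal containers may reveal study status, so masking is partial. The site split in controls depends on what their records contain, which the documents do not say. Changes in pathology practice between the controls and the ICG group are not removed and should be stated as a limitation.
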